14.5 SUBGROUP ANALYSES

Analyses of primary CCI  endpoints will be performed on the following subgroups of patients:

- Age class (<55 years, \geq 55 years),
- Gender (female, male, undifferentiated),
- Region (North America, all other countries together),
- Severity of disease, defined by:
 - % of baseline FEV₁ over personal best FEV₁ post-transplant (baseline FEV₁ >80%, >65–80%, >50–65%, and \leq 50% of personal best FEV₁ post-transplant),
 - baseline FEV₁ % of predicted (<70%, \geq 70%),
 - baseline FEV₁/FVC ratio (< 0.7, \geq 0.7),
 - BLAD at time of personal best post-transplant FEV₁ (Yes, No);
- Race (American Indian or Alaskan Native, Asian, Black or African American, Native Hawaiian or Other Pacific Islander, White, Other).

- Use of azithromycin at randomization (Yes/No)

Subgroup levels may be pooled to have an adequate number (≥ 10) of patients per strata to perform the analysis. Decision on pooling will be taken during the blinded DRM, before data base lock.

Within each subgroup level, descriptive analyses (section 8.1) will be performed on:

- FEV₁,
- FEV₁/FVC,
- Time to Progression of BOS.

FEV₁ and FEV₁/FVC change from baseline will be compared using a two-sample t-test (assuming unequal variances) or, if the required assumptions are not met, a two-sample Mann–Whitney U test.

Comparison of time to progression of BOS curves among treatments will be performed with the log-rank test.

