7.2 Randomization and Stratification

At the Baseline visit (V1), after all inclusion and exclusion criteria have been fully evaluated, eligible patients will be randomized with equal probability to one of two treatment arms, a control arm (SoC alone) and an investigational arm (L-CsA plus SoC). The investigational medicinal product (IMP) is L-CsA. To assure balance between treatment arms with regard to key variables and potential confounders, stratification prior to randomization will be performed for the following variables:

- Screening FEV₁ ≥81% of personal best FEV₁ value post-transplant versus Screening FEV₁ between 80-51% of personal best FEV₁ value post-transplant
- Underlying indication for lung transplant: Chronic obstructive pulmonary disease (COPD) versus all other underlying diseases
- Region: North America versus all other countries together

Within each of the 8 strata, patients will be randomly assigned with equal probability (1:1) to either the investigational or control arm using a permuted blocks randomization. The randomization code, including specification of the block size, will be generated by a statistician not otherwise involved with the trial, using validated software. The unique randomization number and treatment assignment of each patient will be provided to the Investigator through the electronic Case Report Form (eCRF) after eligibility has been verified. The number assigned to a patient will be that patient's unique identifier throughout the clinical trial and cannot be re-assigned to another patient.

This is an open-label clinical trial. Clinical trial monitors, treating physicians, study nurses, study coordinators, and enrolled patients will not be blinded to treatment assignment.

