8.2 Sample Size Considerations

The initial sample size was based on the following considerations. Assuming a treatment group difference for mean FEV₁ change from baseline of 200 mL (0.2 L) and a standard deviation of 350 mL (0.35 L) at the end of treatment Week 48, an independent samples t-test with a one-sided type I error level of $\alpha=0.025$ will have at least 80% power to reject the null hypothesis when the sample size in each treatment group is at least 50 patients. To compensate for a loss of power due to premature withdrawals, a total of 110 patients were initially planned to be randomized.

In accordance with the amended version of the protocol (version 5.0) and following Food and Drug Administration **CCI** [REDACTED]

[REDACTED]
[REDACTED]
[REDACTED]
[REDACTED].

It was anticipated that approximately 160-170 patients have been randomized in BOSTON-2 and approximately 60 patients in BOSTON-1. 169 patients were actually randomized in BOSTON-2 and 62 patients in BOSTON-1.

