14 EFFICACY

For each efficacy analysis, the adequacy of the model assumptions will be checked, and if it is found that these are inadequate then alternative approaches may be performed.

For all variables assumed to be normally distributed, the conditional studentized residuals from this model will be tested using the Shapiro-Wilk test. If the assumption of normality of these residuals is violated, then a log-transformed model will be fitted. The need for a possible log transformation of these variables will be investigated prior to unblinding by assessing the model

residuals without a treatment term. Where data are transformed for analysis, back transformation will be applied for the presentation of results. Presentation of the tables will be amended as needed for this, with the addition of an explanatory footnote.

Classification and imputation of missing data will be completed prior to any transformation of the data for analysis.

As a general remark for all efficacy endpoints based on spirometry data, values collected at 1h and 4h post dose will not be used for any efficacy analyses as they are collected only for safety evaluations.

It is important to note that due to the decrease in sample size (see section 8.2) the study will be underpowered for the assumed effect to assess the statistical hypothesis for the primary endpoint. The statistical modelling for the primary endpoint for the pre-specified covariates may lead to non-convergence of the models and selective covariates will have to be considered. Supplementary analyses for the primary endpoint, **CCI** will adopt simple statistical analyses. As a result, all analysis for this study will be descriptive in nature.

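### SAP 14.5 plans separate treatment tests within subgroup levels in 62 patients, in analyses the SAP calls descriptive, and shows no treatment-by-subgroup contrast

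*SAP*

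**What the plan says.** SAP 14.5 names nine factors: age, gender, region, four measures of disease severity (including BLAD), race, and azithromycin at randomization. Three outcomes are described within each level: FEV1, FEV1/FVC and time to BOS progression. The arms are then compared. For the two spirometry outcomes, "change from baseline will be compared using a two-sample t-test (assuming unequal variances", with a Mann-Whitney test if assumptions are not met. Time to BOS progression is compared by log-rank.

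On small levels the SAP says: "Subgroup levels may be pooled to have an adequate number". The threshold is at least 10 patients per stratum, with no minimum per arm, and pooling is settled at the blinded data review meeting before database lock.

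SAP 14 sets the status of the analyses: "As a result, all analysis for this study will be descriptive in nature". SAP 8.2 gives the size: "169 patients were actually randomized in BOSTON-2 and 62 patients in BOSTON-1".

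The visible text of 14.5 contains no treatment-by-subgroup contrast, no multiplicity statement and no exploratory label.

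**The concern.** Subgroup analyses are normally read for one purpose: whether the treatment effect is consistent across kinds of patient. A p-value within each level does not address that. Significance in one level and not in another can arise from the same true effect, because each level is small and significance depends on its size as much as on the effect. What is needed is the difference between the level-specific effects, with its uncertainty.

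The second issue is volume. Dozens of unadjusted tests on overlapping patients are likely to give some nominally significant results even if L-CsA does nothing. The SAP itself says the study is underpowered, so the overall result may be inconclusive, and a scatter of small subgroup p-values beside it invites selective reading.

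**Working it through.** **Inputs.** 62 patients randomized (SAP 8.2), allocated with "equal probability (1:1) to either the investigational or control arm" (SAP 7.2), so about 31 per arm. Design effect 200 mL, SD 350 mL, one-sided 0.025, which is two-sided 0.05 (SAP 8.2). Factors and levels from SAP 14.5.

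**The plan's own figure.** SAP 8.2 states that the t-test "will have at least 80% power to reject the null hypothesis when the sample size in each treatment group is at least 50 patients". Check: n per arm = 2 x (1.960 + 0.842)² x (350/200)² = 48.1, rounded up to 49. Power at 50 per arm is 81.5% (normal approximation) or 80.8% (noncentral t). The figure reproduces. At 31 per arm the same test has about 60% power.

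**Number of tests.**

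| Factor | Levels listed |
|---|---|
| Age | 2 |
| Gender | 3 |
| Region | 2 |
| Baseline FEV1 as % of personal best | 4 |
| Baseline FEV1 % predicted | 2 |
| Baseline FEV1/FVC | 2 |
| BLAD | 2 |
| Race | 6 |
| Azithromycin | 2 |
| **Total** | **25** |

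With one comparison per outcome per level, the formal ceiling is 25 x 3 = 75. Two pooling scenarios (assumptions):
- Gender to 2 levels, % of personal best to 3, race to 2: 19 levels, 57 tests.
- Gender to 2, % of personal best to 2, race dropped: 16 levels, 48 tests.

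**Chance results with no effect, two-sided 5%.** Expected number = tests x 0.05.
- 48 tests: 2.4
- 57 tests: 2.85
- 75 tests: 3.75

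By symmetry about half would favour L-CsA, so 1.2-1.4 for 48-57 tests. If the tests were independent, the chance of at least one, 1 - 0.95^k, would be 91%, 95% and 98%. They are not independent, since the same patients recur across factors and the outcomes are correlated. A null simulation of 62 patients that allows for this gives about 71-81% for about 52 pooled tests (outcome correlation 0.8 down to 0.3) and about 91% for about 74 unpooled tests (correlation 0.5). The correlations, subgroup proportions and a 40% event rate are assumptions.

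**Typical level: a two-level factor split evenly.** Each level has about 15-16 patients per arm. Noncentral-t power for 200 mL with SD 350 mL is 32.7% at 15 per arm and 34.6% at 16. If the true effect is 200 mL in both levels, the chance that exactly one is significant is 0.327 x (1 - 0.346) + 0.346 x (1 - 0.327) = 0.447, about 45%.

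**Smallest level: 10 patients, 5 v 5.** Power is 12.3%. The 95% CI half-width is t(0.975, 8) x 350 x √(2/5) = 2.306 x 350 x 0.632 = 510 mL, about 2.5 times the design effect.

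**The contrast that answers the question.** For the same even split, the SE of the difference between the two level-specific effects is 350 x √(4/15.5) = 178 mL. The 95% CI half-width is 1.96 x 178 = 348 mL, and power for a 200 mL difference in effect is about 20%.

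**The case against.** The best defence is that 14.5 introduces this work as descriptive, sets no significance threshold or decision rule, and sits in a study whose primary comparison is itself declared descriptive (SAP 14, 14.1.2 and 16). On that view no route leads from a subgroup p-value to a claim. The absence of a decision rule stands. But 14.5 names three tests, and their p-values would appear in the tables. For safety, SAP 15.1 expressly rules out inferential analysis; 14.5 has no such sentence.

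The pooling rule also limits the count. Six race levels of 10 would use 60 of 62 patients, undifferentiated gender is unlikely to reach 10, and the level at or below 50% of personal best lies under the 51% screening floor (Protocol 10.1). This stands: 75 is a ceiling, although pooling is optional.

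The 5 v 5 case is the extreme, and the two-level case is the fairer illustration. Interaction contrasts will also be imprecise, and a hazard ratio may not be estimable in a level where one arm has no events. Both points stand and shape the remedy. SAP 8.1, which 14.5 invokes, already provides Kaplan-Meier event-free rates with 95% intervals, so part of the remedy is in place.

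Finally, SAP 14.3-14.4 are largely redacted, as is part of the opening line of 14.5, so the point covers visible text only.

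**Conclusion.** The point holds as a cheap improvement, not a threat to the trial. The visible plan tests treatment within subgroup levels and provides no estimate of how the effect differs between them. About 48-57 p-values are plausible, with 2.4-2.9 chance results expected if there is no effect. For an evenly split factor, identical true effects would look discordant about 45% of the time.

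These figures assume the pooling described, one time point per outcome, all 62 patients contributing, and the design SD of 350 mL. That SD belongs to the initial sample-size calculation, whereas SAP version 3.0 sets FEV1 to zero after death or re-transplantation for the primary estimand. If 14.5 uses those values, the SD could be larger and the power lower. Missing Week 48 data would also lower it.

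A reader might infer more than the documents support:
- That subgroup effects will be decided by significance. No such rule is stated.
- That 75 tests will be run, or that false positives are certain. The first is a ceiling; the second is likely only.
- That subgroups are the main source of possible spurious findings. Other unadjusted tests are planned in SAP 12.1, 14.2.2 and 14.2.5.1, and nothing ranks them.
- That no interaction analysis exists anywhere. Redaction prevents that conclusion.

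**What to change.** In SAP 14.5:
- For FEV1 and FEV1/FVC, replace the t-test and Mann-Whitney p-values with the estimated treatment difference and 95% CI per level, shown in a forest plot with patients per arm.
- For time to BOS progression, replace the log-rank p-value with Kaplan-Meier event-free rates and 95% CIs by arm, adding a hazard ratio with CI only where both arms have events.
- Add one treatment-by-subgroup contrast with 95% CI per factor, where estimable. For a factor left with more than two levels, name the contrast at the blinded data review meeting.
- Label the whole section exploratory and unadjusted for multiplicity.

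The cost is SAP wording and changed table columns; no new data are needed. The downside is imprecision: a half-width of about 350 mL for an even two-level split, which the intervals will show. Multiplicity is reduced, not removed. With nine factors and three outcomes there are up to 27 contrasts, and 27 x 0.05 = 1.35 intervals would exclude no difference by chance, which is why the exploratory label is needed.

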15 SAFETY DATA

15.1 General Considerations

Summaries of safety data (e.g., AEs, laboratory data, vital signs) will be provided for the SAF. No inferential analyses are planned for safety endpoints.

15.2 Extent of Exposure

15.2.1 Exposure to L-CsA

Exposure to the investigational medicinal product (IMP), L-CsA will be confirmed based on the report of IMP vials returned and dosing recorded in the eCRF. IMP vials that were missing will not be included in the counts of returned (i.e. used) vials; this will also apply where vials are missing but the patients were considered to have taken the vials. A summary table will be prepared including the following details about administration of L-CsA:

- Descriptive statistics for the total vials planned. This is calculated as ([date of last dose – date of randomization + 1] x 2 vials);
- Descriptive statistics for the total actual dose (mg). This is calculated as total empty (used) vials multiplied by dose;
- Descriptive statistics for the duration of treatment in days and weeks. For each patient, the treatment duration will be calculated as the difference between the dates of last and first administration of L-CsA plus 1;

- Descriptive statistics for the duration of treatment in days and weeks, excluding the inhalation temporarily discontinued. For each patient, the treatment duration will be calculated as the difference between the dates of last and first administration of L-CsA plus 1, excluding the days of any inhalation temporarily discontinued. Derivation: (date of last dose – date of first dose + 1) - (stop date of inhalation temporarily discontinued – start date of inhalation temporarily discontinued +1).

Compliance of L-CsA using the drug accountability data is calculated as the total empty (used) vials returned divided by the total vials planned, and will be summarized on the FAS population. For the evaluation of compliance, all the planned vials up to the actual end of treatment for each patient will be considered in the calculation.

By-patient listings will present all IMP administration data.

15.2.2 Exposure to Study treatment (SoC or SoC+L-CsA)

SoC therapy period starts at randomization date and stops at date of study completion or early termination. L-CsA treatment period starts at date of first dose of L-CsA and stops at the date of last dose administered.

Descriptive statistics for the duration of any study treatment (SoC or SoC+L-CsA) in days and weeks will be provided. Since the SoC will cover the entire study period post-randomization, the study treatment duration (SoC or SoC+L-CsA) will be calculated as the difference between the date of study completion/early termination and randomization plus 1.

15.3 Adverse Events

All AEs occurring during the clinical trial, whether or not attributable to study treatment, will be documented in the eCRF. All AEs will be coded to SOCs and PTs using the MedDRA dictionary (version 23.1).

Treatment-emergent adverse events (TEAEs) are defined as AEs with onset on or after the date of randomization.

The Investigator will assess the relationship (unrelated, possible, definite) of each AE to the clinical trial treatment assignment (L-CsA plus SoC or SoC alone). Treatment-related AEs are defined as events the Investigator considers to be possibly or definitely related to clinical trial treatment assignment.

All AEs reported in the eCRF will be presented in by-patient listings for the SAF.

The following summaries will be presented for AEs by treatment group and overall:

- Overview table including the number and percent of patients with
 - AEs;
 - TEAEs;
 - TEAEs leading to discontinuation of study treatment;
 - TEAEs leading study discontinuation;
 - TEAEs leading to death;
 - TEAEs by severity (Mild, Moderate, Severe);
 - Study treatment related TEAEs;
 - Serious TEAEs;
 - Serious study treatment related TEAE;
- TEAEs, grouped within SOC by decreasing frequency of PT;
- TEAEs by decreasing frequency of PT;
- TEAEs leading to discontinuation of study treatment, grouped within SOC by decreasing frequency of PT;
- TEAEs leading to study discontinuation, grouped within SOC by decreasing frequency of PT;
- TEAEs leading to death, grouped within SOC by decreasing frequency of PT;
- TEAEs by maximum severity, grouped within SOC by decreasing frequency of PT;
- TEAEs by relationship, grouped within SOC by decreasing frequency of PT;
- Serious TEAEs, grouped within SOC by decreasing frequency of PT;
- Related serious TEAEs, grouped within SOC by decreasing frequency of PT.

Patients who have multiple events coded to the same PT or within the same SOC will be counted only once in the patient counts for the corresponding summaries, but all events will be considered and listed. Table presentations will contain counts of patients, percentages of patients, and the number of events.

Any AE with missing relationship will be assumed related and summarized in the possible related category to clinical trial treatment assignment. Patients who experience the same event multiple times will be included in the most related category for summarization.

In summaries including severity, the following severity categories will be summarized: ‘Mild’, ‘Moderate’, ‘Severe’. Any AEs with missing severity will be assumed as ‘Severe’. Patients who experience the same event multiple times will be included in the most severe category.

AE summaries will be ordered in terms of decreasing frequency for SOC, and PT within SOC, in the L-CsA plus SoC column.

The following by-patient listings will be provided:

- AEs;
- TEAEs;
- TEAEs leading to discontinuation of study treatment;
- TEAEs leading to study discontinuation;
- TEAEs leading to death;
- Study treatment related TEAEs,
- Serious TEAEs.

These listings will include at least: center, patient identifier, treatment group, AEs (SOC, PT, and verbatim term), AE start date/time, AE end date/time, duration of AE, severity, seriousness, action taken, outcome and relationship.

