#### 13.1.1 Adverse Events (AEs)

##### ***13.1.1.1 Definitions***

###### **Adverse Event (AE)**

An AE is any untoward medical occurrence in a patient after administration of a pharmaceutical product and which does not necessarily have a causal relationship with this treatment. An AE can therefore be any unfavorable and unintended sign (including an abnormal laboratory finding), symptom, or disease temporally associated with the use of a medicinal (investigational) product, whether or not related to the medicinal (investigational) product (ICH Guidelines for Good Clinical Practice, E6(R2), 9 November 2016).

This includes worsening of a pre-existing condition or increase in frequency of a pre-existing condition. An adverse event is considered serious if it meets any of the serious criteria listed below. To ensure no confusion or misunderstanding of the difference between the terms “serious” and “severe”, which are not synonymous, the following clarification is provided:

The term “severe” is often used to describe the intensity (severity) of a specific event (as in mild, moderate, or severe myocardial infarction); the event itself, however, may be of relatively minor medical significance (such as severe headache). This is not the same as “serious”, which is based on patient/event outcome or action criteria usually associated with events that pose a threat to a patient’s life or functioning. Seriousness (not severity) serves a guide for defining regulatory reporting obligations.

The official definition also extends to AEs occurring during the off-treatment follow-up period.

Each patient will be closely observed and questioned for AEs throughout the clinical trial period with non-leading questions (e.g., how do you feel?). The patients will be instructed to report to the clinical trial staff immediately any symptoms and/or signs which occur between the scheduled observation times.

All AEs reported by the patient or observed by the Investigator or hospital personnel will be documented in the respective eCRF. The following information regarding each adverse event will be obtained: date and time of onset and resolution (duration), serious or non-serious (as defined below), severity, treatment required, outcome, relationship to certain medication, and if the AE caused withdrawal from the clinical trial.

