#### ***13.1.1.3 Maximum Intensity***

All adverse events will be graded according to the following:

- **Mild:** Event requiring no special treatment and generally does not interfere with usual activities.
- **Moderate:** Event that impairs usual activities but may be ameliorated by simple therapeutic maneuvers.
- **Severe\*:** Event which impairs usual activities and requires intervention.

\* There is a distinction between a severe adverse event and a serious adverse event; a severe reaction is not a serious adverse event unless it meets one of the criteria for serious events (see [Section 13.1.1.1](#)).

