#### ***13.1.1.4 Serious Adverse Event (SAE) Reporting***

Any serious adverse events occurring

- between the first clinical trial procedure after obtaining informed consent and within 4 weeks after the completion of the EoT visit, whether or not considered related to the clinical trial treatment assignment  
or
- at any time after completion of the last follow-up and coming to the attention of the Investigator, if it is judged as related to the patient's participation in the clinical trial

**must be reported to CCI IMMEDIATELY, but within 24 hours upon knowledge**, as follows:

- Document the event in the eCRF within 24 hours of discovery
- Submit the SAE report by Fax or e-mail to a list of predefined recipients.
- Follow-up the SAE until the outcome is determined, providing periodic updates in the eCRF
- Provide any additional information if requested

Contacts of PPD are as follows:

PPD		PPD	
		PPD	

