## 14.1 Clinical Trial Flow Chart

## 14.2 Visits

### 14.2.1 Screening

Eligible patients who express interest in participating in the trial must sign an IRB/EC approved informed consent form (ICF) prior to initiation of any clinical trial activities. Patients who fulfill all of the inclusion criteria and none of the exclusion criteria may be enrolled into the clinical trial.

Documentation of the patient's consent and eligibility must be completed by the Investigator or his/her designee. All patients who fail the screening activities will be documented in the screening failure log.

The following screening activities will be performed during the screening period (up to 4 weeks prior to Visit 1):

- **Informed Consent:** Obtain informed consent prior to performing any clinical trial activities.
- **Demographics:** Year of birth, gender, ethnic group, date of body measurements, height and weight.
- **Medical History:** Details related to each patient's lung transplant will be recorded and will include: underlying condition (cause of lung failure), date, type of transplantation, donor demographics, donor cause of death, donor/recipient Human Leukocyte Antigen (HLA)-status, induction therapy, antiviral/antifungal/antibacterial therapy, cold ischemia time, donor/recipient CMV-status, donor/recipient Epstein Barr Virus (EBV)-status, acute lung injury. All other significant medical conditions (including GERD) and procedures (including past surgeries) occurring before the ICF is signed will be recorded as medical history. Females will be queried regarding their reproductive histories.
  - **Confirmation of screening FEV1 above -51% of personal best FEV1 value post-transplant.**
  - **Proof of diagnosis** will be recorded.
- **Donor-specific antibody assay:** Collect a blood sample for this assay at the Screening Visit. If DSA test performed within 4 weeks before screening is available, a further DSA test at screening visit will not be mandatory.
- **Inclusion/Exclusion Criteria:** Evaluate eligibility for the clinical trial per the inclusion/exclusion criteria.
- **Serum Pregnancy Test:** Will be obtained in women of childbearing potential (see Appendix II). A serum or urine pregnancy test must be obtained within 7 days prior to randomization.

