##### 15.2.5.2 *Adverse Events*

Adverse events (AEs) will be coded using the Medical Dictionary for Regulatory Activities (MedDRA). Events will be identified as treatment-emergent (TEAE) and non-treatment-emergent (Non-TEAE) on the basis of the date of onset relative to the date of randomization.

Summaries (number and percentage of events as well as of patients with any events of a particular type) of treatment-emergent AEs (by system organ class and preferred term) will be provided. Number (%) of patients experiencing TEAEs by severity, relationship to IMP, seriousness, and action taken with regard to IMP will be summarized. Number (%) of patients with TEAEs leading to discontinuation of clinical trial participation will also be summarized.

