15.4 Acute Tolerability of IMP

At Visit 1, acute tolerability of IMP (L-CsA) during initial dosing will be determined by measuring:

- Spirometry (FEV₁, **CCI** [REDACTED], FVC) measured before and **CCI** [REDACTED].
- Spontaneous report of cough or dyspnea, recorded as AE in the appropriate eCRF.

Descriptive statistics of pre-dose (V1), post-dose (**CCI** [REDACTED]) and change from pre-dose will be presented for each spirometry parameter on the SAF population.

In addition, the number and percent of patients experiencing a decline of **CCI** [REDACTED] in FEV₁ will be presented.

The number and percent of patients experiencing new onset or worsening of TEAEs having the following PTs on the date of the first visit at which L-CsA is administered will be summarized:

- Cough;
- Dyspnea.

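### TEAEs are defined by onset date alone, so a Screening-onset AE kept on one record that worsens or becomes serious after randomization is missing from the TEAE summaries, in either arm

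*SAP*

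**What the plan says.** **TEAE rule.** SAP 15.3: "Treatment-emergent adverse events (TEAEs) are defined as AEs with onset on or after the date of randomization". Protocol 15.2.5.2 likewise sorts events into TEAE and non-TEAE "on the basis of the date of onset relative to the date of randomization". Neither mentions a rise in severity or a change in seriousness.

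**What counts as an AE.** Protocol 13.1.1.1 extends the definition: "This includes worsening of a pre-existing condition or increase in frequency of a pre-existing condition". For each AE the site records "date and time of onset and resolution (duration), serious or non-serious (as defined below), severity" and some further items. The section that defines the grades (13.1.1.3) is headed "Maximum Intensity".

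**When collection starts.** AEs are a Screening item in Protocol 14.2.1. SAEs are reportable "between the first clinical trial procedure after obtaining informed consent and within 4 weeks after the completion of the EoT visit" (Protocol 13.1.1.4). Significant conditions "occurring before the ICF is signed will be recorded as medical history" (Protocol 14.2.1), so an event that begins after consent is an AE and not history. The notes to the Schedule of Activities put Screening at one day to 4 weeks.

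**What is tabulated.** In SAP 15.3, one row of the overview table counts patients with any AE. Every other AE table there is limited to TEAEs. SAP 15.3.1 (infections) and 15.3.2 (malignancies) adopt the TEAE definition. SAP 15.6 summarizes renal terms from AEs without that limit. SAP 15.4 counts patients "experiencing new onset or worsening of TEAEs" of cough or dyspnea on the date of the first visit with L-CsA.

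**The concern.** A TEAE rule normally covers both events that begin on treatment and events already present that get worse on it. This one states only the first half. A cough that is mild in Screening and becomes severe after the first inhalations could keep its Screening onset date and be classed as non-treatment-emergent. It would then be missing from the tables by severity, relationship and seriousness, and from those for events leading to discontinuation or death.

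This matters here because Protocol 9.4.3 names inflamed airways and bronchospasm as the tolerability concern with L-CsA, and Protocol 15.5 gives an adequately sized safety database as the reason for the combined enrolment target. The rule is also out of step with the rest of the SAP's AE handling, which leans towards counting. Under SAP 15.3 a missing severity is set to severe and a missing relationship to related. Under SAP 9.5.3.2 a completely missing start date is imputed to randomization when the other dates allow, which makes the event a TEAE. So an event of unknown onset counts, while one known to have worsened on treatment may not.

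**Working it through.** The plan gives no figure on this point, so the main check sets the rules side by side.

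**Step 1. Follow each kind of event through the rules.**

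| Event | How the documents treat it | TEAE? |
|---|---|---|
| Condition present before consent, worse after randomization | Medical history; the worsening is an AE under Protocol 13.1.1.1, with onset after randomization (endpoint-related worsening is excluded from AEs by 13.1.1.4.4) | Yes |
| AE starts in Screening, worsens after randomization, site opens a new record | New onset date at worsening | Yes |
| Same, site updates the existing record | Onset stays before randomization | No |
| AE starts in Screening, grade unchanged, becomes serious after randomization | 13.1.1.1 speaks of worsening and frequency, not of seriousness, so nothing clearly prompts a new record | No, unless a new record is opened |

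The third and fourth rows are the gap. One onset field, one severity, one seriousness and a maximum-intensity grade fit a single updated record per event, but they do not prove it.

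**Step 2. Check SAP 15.4.** Treatment starts at Visit 1, the randomization visit (Protocol 14.2.2; SAP 9.3). Under SAP 15.3 a TEAE present on that date must have begun on that date. Worsening of a TEAE on the first-dose date can then mean only an event that both began and worsened within one day, unless the first dose was delayed. A cough carried over from Screening on its old record cannot qualify. The worsening half of that count is almost empty.

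**Step 3. See where a missed event still appears.** It appears in the all-AE row of the overview, which gives no preferred term, severity or seriousness. It also appears in the by-patient AE listing, with start date, severity and seriousness. If it carries one of the renal preferred terms, it appears in SAP 15.6.

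**Step 4. Size.** SAP 8.2 reports 62 patients randomized. At 1:1 that is 62 / 2 = 31 per arm, and 1 / 31 = 3.2 percentage points per patient.

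The documents give no AE rate, so the following is illustration only. Assume 4 to 8 AEs per patient-year, 20 to 40% of Screening-onset AEs still ongoing at Visit 1, and 10 to 25% of those worsening.

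- Full 28-day Screening: 62 × 28/365 = 4.76 patient-years.
- Screening-onset AEs: 4.76 × 4 = 19 to 4.76 × 8 = 38.
- Ongoing at Visit 1: 19 × 0.2 = 3.8 to 38 × 0.4 = 15.2.
- Worsening: 3.8 × 0.10 = 0.4 to 15.2 × 0.25 = 3.8 events, both arms together.
- At 14 days of Screening: half of that, 0.2 to 1.9.
- Multiply by the share of worsenings for which no new record is opened. That share is unknown and lies between 0 and 1, so the range runs from 0 to about 4 events.

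A second way: if 2%, 5% or 10% of patients had such an event, that is 31 × 0.02 = 0.6, 31 × 0.05 = 1.6 or 31 × 0.10 = 3.1 patients per arm.

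**The case against.** The strongest reply is that Protocol 13.1.1.1 already closes most of the gap. It makes worsening of a pre-existing condition an AE, and an AE entered at worsening has its own onset date and meets the TEAE rule. On that view the AE definition does not contradict the TEAE rule; it is how worsening gets counted. The eCRF Completion Guidelines (Protocol 21.2) may state the recording practice, and they are not among the documents here. The wording in SAP 15.4 can also be read as assuming that worsening is entered as a TEAE.

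Much of this stands. Worsening of conditions that predate consent is captured this way, and only events that begin inside a window of at most 4 weeks are exposed. Other analyses give partial cover: the renal summary in SAP 15.6, creatinine change from baseline in 15.5.1, and pre- and post-dose spirometry in 15.4. Safety is descriptive (SAP 15.1), and all AEs are listed by patient.

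A reader might infer that on-treatment worsening is lost from every TEAE table, or that the rule hides harm from L-CsA. The documents support neither. The loss depends on the old record being kept, the rule applies to both arms, and bias arises only if worsening differs between them.

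Two things do not fall to the objection. Neither document says whether an ongoing AE that worsens gets a new record, so across about 43 centers classification depends on data-entry habit. And an event that becomes serious without a higher grade is not covered by the wording of 13.1.1.1.

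**Conclusion.** The point holds as a conditional gap in the TEAE definition. A Screening-onset AE that stays on one record and worsens or becomes serious after randomization is a non-TEAE under the stated rule. It is then absent from the TEAE and serious-TEAE tables and from the infection and malignancy summaries. Becoming serious at an unchanged grade is the least protected case. SAP 15.4 also needs correcting, because the rule leaves its worsening count almost empty.

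The number of events is unknown. The illustration of 0 to about 4 rests on assumed rates and on Screening lasting no more than 28 days; zero is possible. The consequence is limited to descriptive safety tables, but with about 31 patients per arm a single reclassified patient can move a row by about 3.2 percentage points. The change is worth making before lock because it is cheap and removes the dependence on site practice.

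**What to change.** 1. **SAP 15.3.** Define a TEAE as an AE that begins on the randomization date or later, or one that begins earlier and rises in severity or becomes serious on that date or later. SAP 15.3.1 and 15.3.2 then follow automatically.
2. **SAP 15.4.** Align the count so that cough or dyspnea that begins, or worsens, at the first L-CsA visit is included whatever its original onset date.
3. **Before lock.** List all AEs with onset in Screening that were still ongoing at Visit 1, and classify each at the blinded data review meeting already planned in SAP 9.2. SAP 15.3.2 sets a precedent, since malignancies are flagged by blinded medical review.
4. **Undetermined timing.** The recorded fields include no date of worsening. If the timing of a moderate, severe or serious event cannot be established, count it as treatment-emergent and footnote it. An event that stayed mild and non-serious remains a non-TEAE, since its highest grade is the lowest there is and it cannot have risen.

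The cost is a sentence or two in the SAP and review of a short listing. The small downside is that a few events of uncertain timing may be counted as TEAEs in both arms. Step 4 limits this by keeping mild, non-serious events out. The change concerns classification for analysis only and touches no dose, treatment or clinical rule.
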